8.3. PHARMACOKINETIC/PHARMACODYNAMIC ANALYSES

The PK/PD analyses will be based on data collected from the scheduled time points of ECG measurement and:

- 1. their corresponding whole blood plitidepsin concentration.
- 2. their estimated whole blood plitidepsin concentration at the corresponding ECG time point by means of population PK modeling.

Evaluable patients (i.e., those who have evaluable ECG data) who withdraw before completing both days (i.e., Days 1 and 15) will be included in these analyses. Plots of individual QTc changes from baseline (Δ QTc) vs. the corresponding plitidepsin blood concentrations will be prepared to explore any concentration-effect relationship for plitidepsin.

The concentration–QTc relationship will be assessed using a linear mixed effects analysis of the relationship between Δ QTc data and plitidepsin concentration according to the equation: Δ QTc = α + β *[plitidepsin], where inter-individual variability will be estimated for both intercept (α) and slope (β). The effect of treatment period (i.e. Day 1 or Day 15) on slope and intercept will also be evaluated. If the intercept term is not significant, the model will be re-fit with a zero intercept term. The predicted value of Δ QTc (along with 90% CI) will be estimated at the mean maximum plasma (C_{max}) values of plitidepsin.

Additionally, in a complementary PK/PD analysis, the relationship between QTc and plitidepsin whole blood concentration will be assessed using linear mixed effect modeling to estimate the maximal change (mean and upper 95% confidence limit) in the QTc associated with therapeutic concentrations of plitidepsin.

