Although the daily variability in QTc interval of cancer patients has not been well described, it may be even larger because enrolled patients are likely to have advanced age, concomitant medical problems and prior QT-prolonging chemotherapy.[5] For this reason, an intrapatient standard deviation of 18 milliseconds is assumed. To reduce intrapatient variability due to measurement error, it has been recommended that the baseline QTc be rigorously investigated and be expressed as the mean of multiple electrocardiogram assessments.[6] For this purpose, two sets of triplicate ECG tracings recorded before plitidepsin administration will be considered baseline assessments: one set before and one after prophylactic medication administration on Days 1 and Day 15.

Electrocardiogram assessments will be performed by means of continuous 12-lead ECG automated digital collection.

All digital ECG continuous recordings will be sent to a third-party central ECG laboratory for measurement of intervals, diagnostics of abnormalities and review of ECG waveform morphology review. This will prevent the potential introduction of bias during the analysis of ECG recordings.

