8. STATISTICAL METHODS

A non-inferiority limit of 20 ms will be used for the comparison of the effects of plitidepsin on the QT/QTc intervals.

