8.1. SAMPLE SIZE

Using a standard deviation of 18 ms in a sample size of 36 evaluable patients, the probability that the upper limit of the one-sided 95% confidence interval (CI) for the difference in mean QTc between each time point and baseline (Δ QTc) will fall below 20 ms is 80%, when the true difference in means equals 5 ms.

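### Dropping a non-significant intercept from the concentration-QTc model can bias the predicted QTc change at Cmax by up to about 2 ms and make its 90% CI too narrow

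*Protocol*

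**What the plan says.** Protocol Appendix 8, section 8.3, regresses ΔQTc on plitidepsin concentration in a linear mixed model, "where inter-individual variability will be estimated for both intercept (α) and slope (β"). It then gives the rule at issue: "If the intercept term is not significant, the model will be re-fit with a zero intercept term". The output is the predicted ΔQTc ("along with 90% CI) will be estimated at the mean maximum plasma" concentration.

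Three things are left open. No significance level is given for the intercept test. It is not said whether the random intercept goes when the fixed one does. The CI is not adjusted for the selection step.

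The setting comes from other sections of the appendix. Section 8.1 plans the substudy "in a sample size of 36 evaluable patients", and section 1.2 says "an intrapatient standard deviation of 18 milliseconds is assumed". Section 2 lists the concentration-QTc relationship among the secondary objectives. The formal decision is in section 8.2: a by-time-point mixed ANOVA judged against 20 ms, with no intercept step. SAP section 8.12 sends the QTc analyses to a separate document, which is not available here.

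**The concern.** The rule is a pretest. It treats failure to reject as proof that the intercept is zero, and then computes the interval as if the zero-intercept model had been chosen in advance.

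There are reasons to expect a non-zero intercept. The substudy has no control arm and no time-matched baseline (Appendix 8, sections 1.2 and 3). Any shift common to the post-dose readings but unrelated to concentration therefore falls into the intercept.

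The baseline rule in section 7.3.2 shows a plausible size. The baseline averages the sets before and after prophylaxis unless the mean of the second is at least 10 ms longer. Suppose prophylaxis raises QTc by d < 10 ms and the effect persists (an assumption). The baseline then contains d/2, and every post-dose ΔQTc carries about +d/2, up to nearly 5 ms.

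At stake is the upper limit for QTc prolongation at Cmax. Section 1.2 says that supratherapeutic exposure cannot be tested safely, so readers are likely to look at this figure.

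**Working it through.** **The plan's own figure.** Section 8.1 gives 80% probability that "the upper limit of the one-sided 95% confidence interval (CI") lies below 20 ms, "when the true difference in means equals 5 ms". Two independent groups of 18 reproduce it: SE = 18 × √(2/18) = 6 ms; (20 − 5)/6 − 1.645 = 0.855; Φ(0.855) = 80.4%. A single within-patient time point gives 97.1% (SE = 18√2/6) or more. This figure belongs to the ANOVA and does not feed the intercept step. The documents give no bias or coverage figure for the concentration model.

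**Inputs from the protocol.** 36 patients; SD 18 ms; 8 post-dose time points on each of 2 days; one Day 1 baseline per patient, the mean of two sets; a slope effect at Cmax set to the 5 ms of section 8.1.

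**Assumed.** Two-sided 5% test; true intercept α from 0 to 8 ms; SD of the slope effect at Cmax 5 ms; between-patient CV of Cmax 50%. The whole-blood profile is computed from the typical values in protocol Table 2 with BSA 1.8 m² and hematocrit 0.33. Relative to Cmax it is 0.84, 1, 0.74, 0.62, 0.49, 0.42, 0.36, 0.19. (Section 8.3 names a plasma maximum for a whole-blood model. That is a separate matter; here the prediction is at the whole-blood Cmax.)

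**Step 1: can the test see the intercept?** A hand approximation that ignores random slopes:
- Baseline error: (18/√2)/√36 = 2.12 ms.
- Regression error: the profile has mean 4.66/8 = 0.5825 and corrected sum of squares 3.220 − 8 × 0.5825² = 0.505 per patient-day, or 36.4 over 72 patient-days. So 18 × √(1/576 + 0.5825²/36.4) = 1.89 ms.
- SE of α ≈ √(2.12² + 1.89²) = 2.84 ms.
- α = 4: z = 1.41, so the test misses it in about 71% of trials. α = 2: z = 0.70, about 89%.

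**Step 2: simulation of the whole rule.** REML fit with random intercept and slope, Wald test of α, refit with α = 0 if not significant, 90% Wald CI at Cmax. 700 runs per row; Monte Carlo SE of coverage about 1 to 1.5 points.

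| True α (ms) | Dropped | Rule, random intercept kept: bias; coverage | Rule, random intercept dropped too: bias; coverage | Intercept always kept: bias; coverage |
|---|---|---|---|---|
| 0 | 95% | +0.05; 85% | −0.13; 85% | −0.03; 88% |
| 2 | 88% | −0.65; 83% | +0.69; 85% | −0.02; 89% |
| 4 | 67% | −1.15; 81% | +0.73; 89% | −0.29; 91% |
| 6 | 36% | −0.67; 80% | +0.76; 91% | −0.03; 90% |
| 8 | 17% | −0.32; 82% | +0.36; 90% | 0.00; 89% |

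At α = 4 with the random intercept kept, the upper limit falls below the true value in 17.1% of trials, against 5.7% when the intercept is always kept (nominal 5%). With the random intercept dropped too it is 4.4%.

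**Step 3: why the sign changes.** With no intercept of any kind, least squares pushes α into the slope. The prediction at Cmax is off by α × (Σc/Σc² − 1) = α × (4.66/3.22 − 1) = +0.45α, which is too high for positive α. With the random intercept kept, it absorbs much of α, the slope stays nearly right, and the prediction omits part of α, which is too low for positive α.

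**Step 4: other assumptions.** Adverse cases, α = 4 or 5 ms, 400 runs each:

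| Case | Random intercept kept: bias; coverage | Dropped too: bias; coverage |
|---|---|---|
| Extra between-patient intercept SD 10 ms | −1.15; 71% | +1.47; 86% |
| Second predose set only as baseline | −1.52; 65% | +1.32; 86% |
| Test at 1% | −1.25; 78% | +1.89; 86% |
| Slope SD 10 ms, Cmax CV 70% | −0.91; 79% | +1.40; 88% |
| Slope SD 0.5 ms, Cmax CV 20% | −0.82; 78% | +0.77; 86% |

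- Only the three PK-matched post-dose points per day (α 0 to 9 ms): absolute bias up to 0.6 ms; coverage 86-89% (kept) or 81-88% (dropped).
- SD 10 ms, α 2 to 4 ms: coverage 82-85% (kept) or 90-92% (dropped).
- A separate generalised least squares check at SD 18 ms, random intercept kept, α 2 to 4 ms: dropped in 62-87% of trials, bias about −1 ms, coverage 75-83%, against about 90% and no bias when the intercept stays.
- Another simulation with smaller residual SD (12 ms), random intercept SD 8 ms and α of 2 to 3 ms in either direction: coverage 73-77%, against 89-92%.

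In every scenario of steps 2 to 4, always keeping the intercept gave coverage of about 86-92%. Where bias was reported, it stayed within 0.3 ms of zero.

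**The case against.** The strongest reply is that little depends on this number. It is a secondary objective, and section 8.3 attaches no threshold to it. The rule "A non-inferiority limit of 20 ms will be used" applies to the by-time-point ANOVA, which includes the end-of-infusion reading. Section 8.2 also tabulates categorical QTc outliers, and section 8.3 plans a complementary mixed model with no stated rule for dropping the intercept. The largest bias found, 1.89 ms, is under a tenth of 20 ms. All of this stands and limits the importance of the point.

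Second, the sources of an intercept are partly controlled: a substudy-specific prophylaxis list, a ban on QT-prolonging drugs, supine rest, standardised meals, a switch of baseline when the prophylaxis shift reaches 10 ms, and a planned check of the period effect on the intercept. A constant intercept would not remove time-of-day effects that vary over the recording either. These points make a large intercept less likely. They do not justify setting a small one to zero on the strength of a weak test.

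Third, the separate QTc analysis document may fix the test level and the random-effect structure, or may keep the intercept. If it keeps the intercept, the point is answered.

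A reader might go further and infer that the interval always covers far less than 90%, or that the result is always falsely reassuring. The documents do not support either. They give no intercept, random-effect variance or test level. Coverage of 65-71% appeared only in two adverse cases with the random intercept kept. For a positive intercept, dropping the random intercept too makes the prediction too high, which is conservative for QT safety.

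**Conclusion.** The point holds as a modest, conditional one. The rule in section 8.3 selects the model on the data and reports an interval that ignores the selection. At the protocol's 36 patients and SD of 18 ms, with an assumed two-sided 5% level, an intercept of 2 to 4 ms is missed in about 60-90% of trials. For a non-zero intercept the bias at Cmax is about 0.3 to 2 ms. Its direction depends on the sign of the intercept and on an unstated choice about the random intercept. Coverage is typically about 75-85% with the random intercept kept, lower under adverse variances, and closer to 90% if it is dropped too. With a true intercept of zero there is essentially no bias. The intercepts and random-effect variances are assumptions, so no single coverage figure can be attached to this trial. The primary by-time-point conclusion against 20 ms is not touched.

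**What to change.** In Appendix 8, section 8.3, replace the refit sentence by a statement that the fixed and random intercept stay in the model whatever the p-value, and that the predicted ΔQTc at Cmax and its 90% CI include the intercept's uncertainty. Show any zero-intercept fit only as a sensitivity analysis. Make the separate QTc analysis document agree. If the analysis has already been run, report both fits.

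If the rule must stay, state the test level and the random-effect structure, and bootstrap the whole procedure, including the selection step.

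The cost is one sentence and a slightly wider interval. In the simulation with residual SD 12 ms the SE was about 1.75 ms with the intercept and 1.5 ms under the rule, so the 90% half-width grows by about 1.645 × 0.25 = 0.4 ms.

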Plitidepsin treatment	-	-	-	-	•	-	-	-	-	-	-	-	٠	-	-	-	-
Meal	-	-	-	-	-	-	-	•	-	-	-	-	-	-	-	•	-

* Patient participation in QT-related polymorphisms assessment is optional. Sample will be collected on Day 1.

** The ECG recorder will be set in place once all safety assessments scheduled for the main study (i.e., vital signs, blood sample extraction for laboratory tests, and ECG) have been conducted.

ECG, electrocardiogram; EOI, end of infusion; IC, Informed Consent; PK, pharmacokinetics.

ECOG	Eastern Cooperative Oncology Group
EMA	European Medicines Agency
EPO	Erythropoietin
FU	Follow-up
G-CSF	Granulocyte Colony Stimulating Factor
h	Hour(s)
Hb	Hemoglobin
HDT	High-dose Therapy
HR	Hazard Ratio
IA	Investigator Assessment
Ig	Immunoglobulin
IDMC	Independent Data Monitoring Committee
IMiD	Immunomodulatory drug
IMWG	International Myeloma Working Group
INR	International Normalized Ratio
IPCW	Inverse Probability of Censoring Weighting
IR	Independent Review
IRC	Independent Review Committee
ISS	International Staging System
ITT	Intention-to-treat
i.v.	Intravenous
IVRS	Interactive Voice Response System
LDH	Lactate Dehydrogenase
LR	Log-rank Test
LVEF	Left Ventricular Ejection Fraction
MedDRA	Medical Dictionary for Regulatory Activities
MM	Multiple Myeloma

MR	Minor Response
MRI	Magnetic Resonance Imaging
MUGA	Multiple-gated Acquisition Scan
NA	Not Applicable
NCI-CTC	National Cancer Institute Common Toxicity Criteria
NE	Not Evaluable
NOS	Not Otherwise Specified
ORR	Overall Response Rate
OS	Overall Survival
PBSC-T	Peripheral Blood Stem Cell Transplantation
PD	Progressive Disease
PFS	Progression-free Survival
PIs	Proteasome inhibitors
PK/PD	Pharmacokinetic/Pharmacodynamic
PR	Partial Response
PS	Performance Status
q4wk	Every Four Weeks
QoL	Quality of Life
RBC	Red Blood Cell
RPSFT	Rank Preserving Structural Failure Time
RR	Response Rate
SAE(s)	Serious Adverse Event(s)
sCR	Stringent Complete Response
SCT	Stem Cell Transplantation
SD	Stable Disease
sFLC	Serum Free Light Chains
SOC	System Organ Class
TTP	Time to Tumor Progression
ULN	Upper Limit of Normal
UK	Unknown
VGPR	Very Good Partial Response
vs.	versus
WBC	White Blood Cells
WHO	World Health Organization
wk	Week
WPC	Worst per Cycle
WPP	Worst per Patient

Treatment Arm A: Plitidepsin in combination with dexamethasone

Treatment Arm B: Dexamethasone alone

1 STUDY RATIONALE

Clinical development of anticancer treatments usually requires combination of more than one active drug for improving efficacy, with each agent having different targets or mechanisms of action in order to prevent or delay the development of tumor resistance. Ideally, from the preclinical point of view, drugs may have shown either additive or synergistic antitumor activity. It is equally important to avoid agents with overlapping toxicity profiles for the development of successful novel combinations.

Plitidepsin (Aplidin[®]) is a novel anticancer compound that has shown activity as a single agent in a recently completed phase II study in relapsed/refractory multiple myeloma (MM) patients. In a first stage, this trial explored the objective response to plitidepsin at 5 mg/m² as a 3-hour i.v. infusion administered every two weeks (q2wk), with 10% of 21 evaluable patients having a partial response (PR) and, additionally, 14% of patients having clinically meaningful disease stabilization (SD \geq 3 months), with a median time to progression (TTP) of 2.3 months. Based on preclinical results that showed additive to synergistic effects of dexamethasone/plitidepsin combination, in a second stage of this phase II trial, patients who experienced suboptimal response (stable disease (SD) or progressive disease (PD)) after three to four plitidepsin infusions were allowed to receive oral dexamethasone 20 mg daily on days 1 through 4 q2wk (160 mg total monthly dose) added to plitidepsin. In this cohort of patients, 28% of the 18 evaluable patients had an objective response and TTP was significantly prolonged to 4.2 months. A similar overall safety profile was found, although with a slight increase in muscular events (mostly myalgia and reversible CPK increase) and a mild decrease in grade 3-4 transaminases increase. Of note, as much as two thirds of these patients had previously received bortezomib, thalidomide or lenalidomide and high-dose therapy (HDT) and peripheral blood stem cell transplantation (PBSC-T), whereas all patients had steroids as part of a prior therapy, with a median of four prior lines of systemic treatments. Although the trial design had limitations that precluded comparison between cohorts, both regimens were well tolerated and showed clinical activity in this heavily pretreated population for which limited clinical options were available. The addition of dexamethasone after three to four cycles of plitidepsin did not change dramatically the response (some disease stabilizations were found in patients who were progressing on plitidepsin alone, and one patient who was stable responded after dexamethasone addition), but responses appeared to be more durable and steeped. Therefore, it seems logical to add dexamethasone to plitidepsin upfront in order to optimize any synergistic effect that may occur clinically to achieve a better and longer disease control.

This approach has been extensively used for most active agents in MM. In fact, corticosteroids have long been a central component of the treatment for MM, with the most commonly used regimens being high-dose dexamethasone alone, melphalan and prednisone, vincristine, doxorubicin, and dexamethasone (VAD), thalidomide, lenalidomide plus dexamethasone, and bortezomib plus dexamethasone. Moreover, dexamethasone can be used as monotherapy as well, the dose and regimen being typically around 20-40 mg on days 1-4, 9-12, and 17-20 of a 28- to 35-day cycle for a total of 240-480 mg per cycle, although adverse reactions may be observed including principally endocrine axis suppression, serious infection derived from clinically relevant immunosuppression, and confusion or mood changes including acute psychosis. In fact,

dose of dexamethasone has recently raised some concerns particularly after the Eastern Cooperative Oncology Group (ECOG) 4A03 study. The ECOG, compared the administration of lower doses of dexamethasone (40 mg d 1, 8, 15, and 22 p.o. q4wk, for a total monthly dose of 160 mg) plus lenalidomide with high-dose dexamethasone at the usual dose (40 mg d 1-4, 9-12, and 17-20 p.o. q4wk, for a total monthly dose of 480 mg) plus the same lenalidomide regimen, and reported a significant improvement in overall survival with a better safety profile for the lower dose arm. A second study with lenalidomide plus dexamethasone in the relapsed/refractory setting showed that patients who had dose reductions of dexamethasone have shown a significantly higher overall response rate, including a higher complete response, progression-free survival (PFS) and improved median overall survival, when compared to those who received dexamethasone at the assigned dose, with adverse events rates comparable between both groups. Finally, and based on data from last available publications on dexamethasone and bortezomib combinations, dexamethasone administered at reduced doses (20 mg) the same day and the day after bortezomib infusion up to a total dose of 160 mg/cycle, has been associated with a better safety profile while maintaining the same level of activity.

2 STUDY DESIGN

This will be a prospective, multicenter, open-label, two-arm, 2:1 randomized phase III study of plitidepsin in combination with dexamethasone vs. dexamethasone alone in patients with relapsed/refractory MM.

The primary study endpoint is progression free survival (PFS).

- Treatment Arm A:
 - Dexamethasone: 40 mg orally on Day 1, 8, 15 and 22 every four weeks (q4wk) at least one hour before plitidepsin infusion.
 - Plitidepsin: 5 mg/m² intravenously (i.v.) diluted to a total volume of 250 ml in 0.9% saline via a central venous catheter (suggested) or diluted to a total volume of 500 ml in 0.9% saline via a peripheral line. Infusion will be performed through a pump device over three hours (fixed rate) on Day 1 and 15 q4wk.

- Treatment Arm B:
 - Dexamethasone: 40 mg orally on Day 1, 8, 15 and 22 q4wk.

Patients in the control arm (dexamethasone alone, Arm B) who have documented disease progression after a minimum of eight weeks from randomization should be offered to cross over to combination arm (plitidepsin + dexamethasone, Arm A) upon Sponsor agreement.

Patients may be treated with additional cycles of plitidepsin and dexamethasone or dexamethasone alone, as long as no unacceptable toxicity and/or disease progression is documented.

3 OBJECTIVES AND ENDPOINTS

3.1 Primary objective

- To compare the efficacy of plitidepsin in combination with dexamethasone *vs.* dexamethasone alone as measured by progression-free survival (PFS) in patients with relapsed/refractory multiple myeloma (MM).

3.2 Secondary objectives

- To evaluate tumor response according to the international myeloma working group (IMWG) criteria.
- To assess duration of response (DR) and overall survival (OS).
- To assess efficacy in patients who undergo crossover from dexamethasone alone to plitidepsin and dexamethasone combination.
- To characterize and compare the safety profile on both arms in this population.
- To characterize the pharmacokinetics (PK) and pharmacokinetic/pharmacodynamic (PK/PD) relationship.

3.3 Endpoints

Primary endpoint:

- PFS, according to independent review committee (IRC) assessment, as per intention-to-treat (ITT) analysis.

Secondary endpoints:

- Objective RR.
- Best overall response including rate of minor response (MR) or better (according to the IMWG criteria).
- Response and progression-free survival to combination treatment in patients who crossed over after progression on dexamethasone alone.
- Time-to-event endpoints: DR and OS.
- Safety as per-protocol will be evaluated in each arm separately. Adverse events (AEs) will be graded according to the National Cancer Institute Common Terminology Criteria for Adverse Events (CTCAE), version 4.
- PK/PD parameters.

4 PATIENTS EVALUABILITY CRITERIA

The study population will include patients who have relapsed or refractory MM after all standard available therapy. To be enrolled in this study, the patients must meet all inclusion criteria and no exclusion criteria.

4.1 Analysis sets definitions

“All Randomized Patients” analysis set is defined as all patients who are randomized to either treatment arm, independent of whether they received the study drug.

“All Treated Patients” analysis set is defined as all randomized patients who receive at least part of one dose or infusion of the investigational agents.

“All Evaluable Patients” analysis set is defined as all randomized patients who have completed at least one full cycle of treatment or have received two incomplete cycles followed by at least one response assessment not less than eight weeks (\pm one week) after treatment onset. Patients withdrawn from the study due to early disease progression or treatment-related toxicity will be considered as “early progression” or “treatment failure”, respectively, even though they have not received a full cycle. Patients withdrawn due to significant clinical deterioration of unknown reason, hypersensitivity reactions, or refusal to continue on study for any reason or unrelated AEs without any disease assessments after the start of study treatment or those patients with a protocol deviation resulting in an impossibility of drawing conclusions about the efficacy of the study therapy will be considered not evaluable for efficacy and their response will be categorized as “non evaluable”.

“All Responder Patients” analysis set is defined as all evaluable patients who have minor response or better as overall best response.

“All Crossover Patients” analysis set is defined as all patients randomized to Arm B who have documented disease progression after their eighth week from randomization and cross over to Arm A.

